#### *Planned Sensitivity Analyses*

##### 1. Best-Likely-Case Scenario for Missing Data

- o For patients missing baseline quality of life, set the baseline quality of life equal to the mean baseline value for the appropriate stratum of the population. Population to be stratified based on type of surgery (cardiac versus non-cardiac) and history of falls.
- o For patients in the intervention group missing one-year quality of life, set the quality of life value equal to the maximum postoperative quality of life within the patient's stratum (still stratified by type of surgery and history of falls).
- o For patients in the control group missing one-year quality of life, set the quality of life value equal to the minimum postoperative quality of life within the patient's stratum (still stratified by type of surgery and history of falls).
- o Patients who die before one year will be excluded.

##### 2. Worst-Likely-Case Scenario for Missing Data

- o For patients missing baseline quality of life, set the baseline quality of life equal to the mean baseline value for the appropriate stratum of the population. Population to be stratified based on type of surgery (cardiac versus non-cardiac) and history of falls.
- o For patients in the control group missing one-year quality of life, set the quality of life value equal to the maximum postoperative quality of life within the patient's stratum (still stratified by type of surgery and history of falls).

- For patients in the intervention group missing one-year quality of life, set the quality of life value equal to the minimum postoperative quality of life within the patient's stratum (still stratified by type of surgery and history of falls).
- Patients who die before one year will be excluded.

3. Expanded Control Group with Matched Cohort

- Each patient randomized in the ENGAGES trial will be matched to a patient enrolled in the SATISFY-SOS study.
  - All patients enrolled in SATISFY-SOS who meet the following criteria will be considered.
    - Age 60 or older
    - Hospital stay  $\geq$  2 days
    - Surgery between January 2015 and May 2018 (same dates as ENGAGES)
  - For each patient meeting the above criteria, a propensity score for enrollment in the ENGAGES trial will be constructed using logistic regression. Covariates included in the model will include age, sex, ASA physical status, surgery type (cardiac versus non-cardiac), and history of falls.
  - (Because all patients enrolled in ENGAGES were co-enrolled in SATISFY-SOS, the population described above will include all patients who were enrolled in ENGAGES.)
  - Patients enrolled in ENGAGES will be matched 1:1 without replacement to SATISFY-SOS patients not enrolled in ENGAGES based on the logit of the propensity score. A greedy nearest-neighbor algorithm will be used, with a maximum caliper width of  $0.2 * \text{the standard deviation in the logit of the propensity score}$ .
  - Use the same model structure described above.
  - Add a variable to Z indicating whether the patient was enrolled in ENGAGES.

4. Patient-Reported Subjective Quality of Life Change

- Analysis to include the subset of patients enrolled in ENGAGES who returned the SATISFY-SOS survey at one year
  - The survey includes a question asking if quality of life is better, the same, or worse compared to before surgery
- Use a chi square test to compare whether patients in the intervention group were more likely to rate their quality of life as "better" the before surgery, compared to patients in the control group.

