***Hypothesis 3: Is EEG Guidance Intervention Associated with Fewer Falls One Year After Surgery?***

*Patient Population:* Patients randomized to intervention or control (N = 1232)

*Primary Predictor Variable:* EEG guidance intervention

(X=0 for control or X=1 for intervention)

Intention to treat

*Outcomes:* Presence or absence of fall(s) during the one-year postoperative follow-up period, measured via patient report one the one-year ENGAGES survey

- Patients who did not fill out the survey (including both living non-respondents and deceased patients) will be excluded

*Data Description Plan:* Confusion matrix of falls versus EEG guidance intervention

*Analysis Plan:* Logistic regression

- Will perform unadjusted and adjusted analyses
- Will adjust for age, sex, American Society of Anesthesiologists (ASA) physical status classification (1-3 vs 4-5), number of comorbid conditions, history of falls (yes/no within previous 6 months), evidence of abnormal cognition (preoperative Short Blessed Test score > 4), surgery type (cardiac versus non-cardiac), length of anesthesia (Anesthesia Stop – Anesthesia Start)
  - o Note that ASA is dichotomized in this analysis, and functional capacity <4 METS has been dropped. These changes were made to reduce the number of degrees of freedom in the model, with the goal of having one degree of freedom per 10 patients who fell.
  - o Multiple imputation may be used to address missing values of these variables

*Planned Sensitivity Analyses*

1. Deceased Patients
  - o Assume all patients who die within one year have fallen.
2. Best-Case Scenario for Missing Data
  - o Assume all patients who die within one year have fallen.
  - o Assume that living patients in the intervention group with missing fall outcome data have not fallen. Assume that living patients in the control group with missing fall outcome data have fallen.
3. Worst-Case Scenario for Missing Data
  - a. Assume all patients who die within one year have fallen.
  - b. Assume that living patients in the intervention group with missing fall outcome data have fallen. Assume that living patients in the control group with missing fall outcome data have not fallen.
4. Expanded Control Group with Matched Cohort
  - o Use the same matched cohort as described above in Hypothesis 2.
  - o Perform a logistic regression as described above, also adjusting for whether the patient was enrolled in ENGAGES.
5. Number of Falls

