  - o For patients who completed the SATSIFY-SOS 1-year survey, we have a categorical variable detailing the number of falls (0, 1, 2, or 3+).
  - o Perform an ordinal logistic regression, adjusting for the variables described above.

*Exploratory Analyses:*

1. Is duration of intraoperative EEG suppression (minutes with suppression ratio > 1%) associated with mortality?
  - a. Cox proportional hazards model, adjusting for same variables as in hypothesis #1
  - b. Instrumental variable analysis will be used to account for the EEG intervention

2. Is duration of intraoperative EEG suppression (minutes with suppression ratio > 1%) associated with worse quality of life at one year?
  - a. Generalized linear model, same structure as in hypothesis #2
  - b. Instrumental variable analysis will be used to account for the EEG intervention
3. Is duration of intraoperative EEG suppression (minutes with suppression ratio > 1%) associated with more falls at one year?
  - a. Logistic regression, adjusting for same variables as in hypothesis #3
  - b. Instrumental variable analysis will be used to account for the EEG intervention
4. Is duration of intraoperative BIS < 40 associated with mortality?
  - a. Cox proportional hazards model, adjusting for same variables as in hypothesis #1
  - b. Instrumental variable analysis will be used to account for the EEG intervention
5. Is duration of intraoperative BIS < 40 associated with worse quality of life at one year?
  - a. Generalized linear model, same structure as in hypothesis #2
  - b. Instrumental variable analysis will be used to account for the EEG intervention
6. Is duration of intraoperative BIS < 40 associated with more falls at one year?
  - a. Logistic regression, adjusting for same variables as in hypothesis #3
  - b. Instrumental variable analysis will be used to account for the EEG intervention
7. Is median intraoperative end-tidal anesthetic concentration value (measured in MAC) associated with mortality?
  - a. Cox proportional hazards model, adjusting for same variables as in hypothesis #1
  - b. Instrumental variable analysis will be used to account for the EEG intervention
8. Is median intraoperative end-tidal anesthetic concentration value (measured in MAC) associated with worse quality of life at one year?
  - a. Generalized linear model, same structure as in hypothesis #2
  - b. Instrumental variable analysis will be used to account for the EEG intervention

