Research Design Overview (See Figure 2)

The Human Research Protection Office at Washington University School of Medicine has approved the study. This protocol, which details the design of the ENGAGES study, includes all the elements elaborated in the SPIRIT (Standard Protocol Items: Recommendations for Interventional Trials) checklist.^{51,52} The ENGAGES study will be a pragmatic randomized clinical trial enrolling 1,232 patients 60 years and older who will undergo elective major surgery at Barnes Jewish Hospital, St. Louis, MO. This hospital is an academic medical center in the Midwestern United States, which is affiliated to Washington University School of Medicine and serves a diverse range of patients in St. Louis and its environs. Eligible patients will often be recruited through the Center for Preoperative Assessment and Planning (CPAP) clinic at Barnes Jewish Hospital. Surgical patients might also be enrolled on hospital wards prior to their surgery. Participants will be randomly assigned to receive the electroencephalography-guided protocol or routine care. Assessments will be conducted at baseline, in the postoperative period during the hospital stay, at 30 days and at 1-year post-surgery. The primary outcome measure will be the incidence of postoperative delirium. During the 1-year follow-up period, health-related quality of life information and information on incident falls will be collected. At Washington University, surgical patients have been enrolled in the **Systematic Assessment and Targeted Improvement of Services Following Yearly Surgical Outcomes Surveys** (SATISFY-SOS - NCT02032030) study since 2012. For the exploratory aim 3, there will be a prospective comorbidity-matched cohort study using the ENGAGES clinical trial population and reference subjects from the ongoing SATISFY-SOS study. There is ongoing rolling enrollment of participants to the SATISFY-SOS study, and information on patients is continuously being collected, updated and stored in a SQL Server database (Microsoft®, Redmond, WA) hosted by the Institute of Quality Improvement, Research and Informatics at Washington University.

Figure 2: Flow diagram showing design overview for ENGAGES study

Study Subjects

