This study proposes to enroll 1,232 patients who are already enrolled in the SATISFY-SOS study. Patients 60 years old and older, who are competent to provide informed consent and who are undergoing major elective surgery under general anesthesia with a potent volatile anesthetic agent that requires a minimum stay of 2 days postoperatively (e.g., open cardiac surgery, open thoracic surgery, major vascular surgery, intra-abdominal surgery, open gynecologic surgery, open urologic surgery, major orthopedic surgery, open hepatobiliary surgery and major ear, nose and throat surgery) will be eligible for inclusion. As there are no absolute contraindications to EEG monitoring, the ENGAGES study is designed as a practical trial that will have minimal exclusions and therefore maximum applicability. Neurosurgical procedures will be excluded as surgery on the brain can confound the outcome (postoperative delirium). We will also exclude patients with preoperative delirium and patients who are unable to participate adequately in delirium screening including those who are blind, deaf, or illiterate or not fluent in English. Patients with a history of intraoperative awareness during intended general anesthesia will also be excluded.⁵³ Patients will be excluded if, prior to their index surgery, a second surgery is planned to occur within five days after the index surgery. Figure 3 outlines the flow of participants in the ENGAGES study.

Figure 3: Flow of participants

to the pilot phase of the ENGAGES trial during the first year. In years 2-4 an accrual rate of 300 to 400 patients per year is anticipated. To maximize efficiency, data from the pilot will be included in the main study.⁵⁴ In this pilot cohort, practical aspects of the trial's conduct will be evaluated. These include the feasibility of enrolling adequate numbers of patients in the preoperative assessment clinic; the ability of researchers to conduct the baseline preoperative assessments; the demonstration of retrieval of complete perioperative data (including repeated measures of EEG-derived parameters) from the electronic medical record; successful daily postoperative delirium assessments until postoperative day 5 or hospital discharge; for patients that remain delirious at day 5 they will be assessed until they return to baseline or until postoperative day 10, and near complete (>80%) 30-day patient reported outcomes data.

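### The SATISFY-SOS matched cohort applies only part of ENGAGES eligibility, has no comorbidity term in its score and names no falls source, so the ENGAGES-versus-SATISFY-SOS coefficient cannot isolate the safety intervention

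*SAP*

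**What the plan says.** The SAP's Hypothesis 2, sensitivity analysis 3 (Expanded Control Group with Matched Cohort) matches ENGAGES patients 1:1 to SATISFY-SOS patients outside the trial. On the pool it says "All patients enrolled in SATISFY-SOS who meet the following criteria will be considered", and it lists three: "Age 60 or older", a hospital stay of at least 2 days, and "Surgery between January 2015 and May 2018 (same dates as ENGAGES"). On the propensity score it says "Covariates included in the model will include age, sex, ASA physical status, surgery type (cardiac versus non-cardiac), and history of falls". The outcome model then keeps the Hypothesis 2 structure and gains an indicator for enrollment in ENGAGES. Hypothesis 3, sensitivity analysis 4 reuses the same cohort and the same indicator for falls.

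The protocol's Research Design Overview says of Aim 3 that "there will be a prospective comorbidity-matched cohort study using the ENGAGES clinical trial population" and SATISFY-SOS reference subjects. Its Study Subjects section limits ENGAGES to elective major surgery under volatile general anesthesia and adds "Neurosurgical procedures will be excluded as surgery on the brain can confound the outcome (postoperative delirium"). It also excludes preoperative delirium, inability to take part in delirium screening, previous intraoperative awareness, and a second operation already planned within five days.

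Falls in SAP Hypothesis 3 are "measured via patient report one the one-year ENGAGES survey". The SAP treats the SATISFY-SOS survey as a separate instrument. For patients who completed that one, "we have a categorical variable detailing the number of falls (0, 1, 2, or 3" or more).

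**The concern.** Under the protocol's section on the secondary intervention, every ENGAGES patient in both arms is to receive the safety intervention and the matched SATISFY-SOS patients are not. Randomization therefore says nothing about its effect. In the SAP, only the coefficient on the ENGAGES indicator speaks to Aim 3, and that coefficient absorbs every other difference between the cohorts.

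Three such differences are left open. Matched patients may be of a kind that ENGAGES would not have enrolled. Comorbidity is not matched, despite the protocol's description. And the falls outcome, read literally, is undefined for patients who never received an ENGAGES survey. A reported benefit or harm of the safety intervention could then be case mix or ascertainment.

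**Working it through.** **1. The plan's nearest figure.** The documents give no number for the matched comparison. The closest is the protocol's falls power: 40% versus 28%, 500 per arm, two-sided 0.05, stated as above 80%. With mean risk 0.34:

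- SE under the null = √(2×0.34×0.66/500) = 0.02996
- SE under the alternative = √((0.40×0.60+0.28×0.72)/500) = 0.02972
- z = (0.12 − 1.96×0.02996)/0.02972 = 2.06, so power is 98.0%

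The stated bound is met. It concerns the EEG comparison and is not at issue here.

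**2. Eligibility, side by side.**

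| ENGAGES rule | In the SAP pool? | In the score or outcome models? |
|---|---|---|
| Age 60 or more | Yes | Yes |
| Stay of 2 days or more | Yes | No |
| Elective | No | No |
| Major surgery types | No | Cardiac versus non-cardiac only |
| Volatile general anesthesia | No | No (duration of anesthesia only, adjusted models) |
| No neurosurgery | No | No; would count as non-cardiac |
| Delirium, screening, awareness and second-surgery exclusions | No | Abnormal cognition only, adjusted models |

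Comorbidity count is absent from the score and from the unadjusted models, but present in the adjusted ones. ASA status, a coarse proxy, is in the score. The adjusted falls model drops functional capacity and reduces ASA to two levels.

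**3. Which coefficient is exposed.** Let X be EEG guidance and E the ENGAGES indicator. Without covariates, logit(p) = β0 + γE + β1X fits three groups exactly:

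- γ = logit(p, ENGAGES control) − logit(p, matched)
- β1 = logit(p, ENGAGES intervention) − logit(p, ENGAGES control)

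Matched patients do not enter β1. With a covariate this was checked on 400 simulated data sets with no true effect. Responders were 986 ENGAGES (0.80×1,232) and 813 matched (0.66×1,232); the two rates are the protocol's one-year completion assumption and its reported SATISFY-SOS response. Two assumptions were added: an unmatched risk factor (log odds ratio 0.4 per SD) lying 0.4 SD higher in the matched cohort, and 20% of falls missed there.

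| Fit | Coefficient | Mean estimate (true value 0) |
|---|---|---|
| Trial only | EEG | 0.005 (SE 0.133) |
| Expanded, indicator kept | EEG | 0.004 (SE 0.132) |
| Expanded, case mix only | ENGAGES | −0.16 |
| Expanded, case mix plus missed falls | ENGAGES | +0.22 |
| Expanded, indicator dropped | EEG | +0.14 |

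The −0.16 is the product of the inputs, −(0.4×0.4). The added patients leave the EEG standard error almost unchanged.

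**4. Possible size for falls.** Each line assumes no true difference. The 40% risk is the protocol's assumption; the other ranges are mine unless stated.

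- Case mix: shift = ineligible share × risk gap. From 5% × 10 points = 0.5 to 30% × 20 points = 6. If ineligible patients fall more often, ENGAGES looks better; if less often, worse.
- Capture: if the matched cohort's survey records a fraction s of the falls the ENGAGES survey would, shift = 40 × (1 − s). For s = 0.95, 0.90, 0.80 and 0.70 this is 2, 4, 8 and 12 points against ENGAGES. With 986 and 813 responders, the chance of p<0.05 is 14%, 41%, 94% and about 100%.
- Response: shift = difference in non-response × excess risk in non-respondents. With 66% and about 80% response, (0.34 − 0.20) × 5 = 0.7 to (0.34 − 0.20) × 10 = 1.4 points, also against ENGAGES.

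**The case against.** The strongest reply is that the SAP presents this as a sensitivity analysis of EEG guidance and states no hypothesis on the ENGAGES indicator. A reader might infer that the extra controls bias the EEG comparison. The documents do not support that: the SAP puts the indicator in both matched models, and step 3 shows that the EEG coefficient then rests on the randomized arms. That part of the reply stands in full.

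Second, much adjustment is already planned. The adjusted quality-of-life model has comorbidity count, functional capacity, cognition and a spline on baseline VR-12; the adjusted falls model has comorbidity count and cognition. This stands, and it makes the missing comorbidity term the lesser part of the concern. It does not help with urgency, anesthetic technique or neurosurgery, for which no model has a term.

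Third, the protocol does describe a shared route for falls. Its sections on the secondary intervention, on postoperative health and wellbeing, and on the falls outcome point to SATISFY-SOS for ENGAGES patients and matched controls alike. A mix of surveys is therefore possible rather than established. The gap is that the SAP names a different survey and does not invoke that route.

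Fourth, a reader might infer that the comparison group is sicker. The documents give neither the pool's composition nor SATISFY-SOS's own entry rules, and several of the unapplied exclusions, such as previous awareness or language, do not imply worse health. The neurosurgery exclusion was justified by delirium; its bearing on falls and quality of life is indirect, through the protocol's own link from delirium to both.

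Finally, the protocol's Aim 3 methods text is cut off in the copy available, so its full matching list cannot be checked. The SAP's list is complete.

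**Conclusion.** The concern holds for one coefficient. The matched pool carries over ENGAGES' age and 2-day-stay rules and adds surgery dates, but not the elective, major-surgery, volatile-anesthesia or non-neurosurgical rules, and nothing later in the analysis can make up for that. The missing comorbidity term contradicts the protocol's description and is partly mitigated. The falls source for matched patients is unstated.

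The ENGAGES-versus-SATISFY-SOS coefficient therefore cannot separate the safety intervention from patient type or, if the sources differ, from survey. The figures in step 4 show what could happen under assumed inputs; they are not estimates, and the simulated coefficient changed sign between scenarios. The EEG conclusions are not in question. This is worth correcting because it is cheap, and because this coefficient is the SAP's only evidence on an exploratory aim.

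**What to change.** 1. Restrict the SATISFY-SOS pool to patients who meet the ENGAGES criteria identifiable in the perioperative record: elective, the listed major surgery types, volatile general anesthesia, non-neurosurgical. State which other exclusions cannot be identified.
2. In the matched falls analysis, take the falls answer from the SATISFY-SOS one-year survey in both cohorts, and report response by cohort. A common source does not remove a response difference if extra calls raise returns among ENGAGES patients.
3. Add number of comorbid conditions to the propensity model, in line with the protocol. This gains less than items 1 and 2.
4. Keep the ENGAGES indicator in every matched fit, and label its coefficient observational.

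The cost is SAP wording and programming on data that the protocol describes as already held in the department's repository, assuming that urgency, procedure and anesthetic technique can be read from it. The pool becomes smaller, a few more ENGAGES patients may go unmatched, and those without a SATISFY-SOS survey drop out of the matched falls analysis.

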***Hypothesis 3: Is EEG Guidance Intervention Associated with Fewer Falls One Year After Surgery?***

*Patient Population:* Patients randomized to intervention or control (N = 1232)

*Primary Predictor Variable:* EEG guidance intervention

(X=0 for control or X=1 for intervention)

Intention to treat

*Outcomes:* Presence or absence of fall(s) during the one-year postoperative follow-up period, measured via patient report one the one-year ENGAGES survey

- Patients who did not fill out the survey (including both living non-respondents and deceased patients) will be excluded

*Data Description Plan:* Confusion matrix of falls versus EEG guidance intervention

*Analysis Plan:* Logistic regression

- Will perform unadjusted and adjusted analyses
- Will adjust for age, sex, American Society of Anesthesiologists (ASA) physical status classification (1-3 vs 4-5), number of comorbid conditions, history of falls (yes/no within previous 6 months), evidence of abnormal cognition (preoperative Short Blessed Test score > 4), surgery type (cardiac versus non-cardiac), length of anesthesia (Anesthesia Stop – Anesthesia Start)
  - o Note that ASA is dichotomized in this analysis, and functional capacity <4 METS has been dropped. These changes were made to reduce the number of degrees of freedom in the model, with the goal of having one degree of freedom per 10 patients who fell.
  - o Multiple imputation may be used to address missing values of these variables

*Planned Sensitivity Analyses*

1. Deceased Patients
  - o Assume all patients who die within one year have fallen.
2. Best-Case Scenario for Missing Data
  - o Assume all patients who die within one year have fallen.
  - o Assume that living patients in the intervention group with missing fall outcome data have not fallen. Assume that living patients in the control group with missing fall outcome data have fallen.
3. Worst-Case Scenario for Missing Data
  - a. Assume all patients who die within one year have fallen.
  - b. Assume that living patients in the intervention group with missing fall outcome data have fallen. Assume that living patients in the control group with missing fall outcome data have not fallen.
4. Expanded Control Group with Matched Cohort
  - o Use the same matched cohort as described above in Hypothesis 2.
  - o Perform a logistic regression as described above, also adjusting for whether the patient was enrolled in ENGAGES.
5. Number of Falls
  - o For patients who completed the SATSIFY-SOS 1-year survey, we have a categorical variable detailing the number of falls (0, 1, 2, or 3+).
  - o Perform an ordinal logistic regression, adjusting for the variables described above.

*Exploratory Analyses:*

1. Is duration of intraoperative EEG suppression (minutes with suppression ratio > 1%) associated with mortality?
  - a. Cox proportional hazards model, adjusting for same variables as in hypothesis #1
  - b. Instrumental variable analysis will be used to account for the EEG intervention

2. Is duration of intraoperative EEG suppression (minutes with suppression ratio > 1%) associated with worse quality of life at one year?
  - a. Generalized linear model, same structure as in hypothesis #2
  - b. Instrumental variable analysis will be used to account for the EEG intervention
3. Is duration of intraoperative EEG suppression (minutes with suppression ratio > 1%) associated with more falls at one year?
  - a. Logistic regression, adjusting for same variables as in hypothesis #3
  - b. Instrumental variable analysis will be used to account for the EEG intervention
4. Is duration of intraoperative BIS < 40 associated with mortality?
  - a. Cox proportional hazards model, adjusting for same variables as in hypothesis #1
  - b. Instrumental variable analysis will be used to account for the EEG intervention
5. Is duration of intraoperative BIS < 40 associated with worse quality of life at one year?
  - a. Generalized linear model, same structure as in hypothesis #2
  - b. Instrumental variable analysis will be used to account for the EEG intervention
6. Is duration of intraoperative BIS < 40 associated with more falls at one year?
  - a. Logistic regression, adjusting for same variables as in hypothesis #3
  - b. Instrumental variable analysis will be used to account for the EEG intervention
7. Is median intraoperative end-tidal anesthetic concentration value (measured in MAC) associated with mortality?
  - a. Cox proportional hazards model, adjusting for same variables as in hypothesis #1
  - b. Instrumental variable analysis will be used to account for the EEG intervention
8. Is median intraoperative end-tidal anesthetic concentration value (measured in MAC) associated with worse quality of life at one year?
  - a. Generalized linear model, same structure as in hypothesis #2
  - b. Instrumental variable analysis will be used to account for the EEG intervention
9. Is median intraoperative end-tidal anesthetic concentration value (measured in MAC) associated with more falls at one year?
  - a. Logistic regression, adjusting for same variables as in hypothesis #3
  - b. Instrumental variable analysis will be used to account for the EEG intervention
10. Is the EEG guidance intervention associated with higher (better) Barthel Index at one year?
  - a. Will only be available for patients who return the SATISFY-SOS survey
  - b. Mann Whitney U test (because we expect a skewed distribution)
11. Is the EEG guidance intervention associated with a higher rate of return to work at one year?
  - a. Will only be available for patients who return the SATISFY-SOS survey
  - b. Chi-square test for dichotomous return to work (yes/no)
  - c. Among patients who return to work, Mann Whitney U test for number of months before the patient returned to work
